Study Protocol and Statistical Analysis Plan:

Evidence of the Advantages of Preoperative Intra-aortic Balloon Pump in Surgical Revascularization of Acute Myocardial Infarction

Brief Title: Use of Intra-aortic Balloon Pump Before Surgery for Acute Myocardial Infarction

NCT number: NCT06468982

Document date: May 1, 2021

Evidence of the Advantages of Preoperative Intra-aortic Balloon Pump in Surgical Revascularization of Acute Myocardial Infarction

Patients hospitalized due to acute myocardial infarction (AMI) and scheduled for coronary artery bypass grafting (CABG) surgery based on the decision of the Cardiology and Cardiovascular Surgery council will be included in this prospective observational cohort study. Based on their clinical conditions, the patients will be categorized into two groups: Group A, comprising those receiving intra-aortic balloon pump (IABP) support, and Group B, comprising those not receiving IABP support.

The patients' anamnesis, medical history, physical examination findings, laboratory results, and EuroScore-II scores will be meticulously recorded. Details of the assessments are as follows:

Assessment of Chest Pain (Angina): Chest pain severity will be evaluated on the first day of admission using a scoring system based on the Wong-Baker FACES® pain scale (0–10; Wong-Baker FACES Foundation; https://wongbakerfaces.org). For patients in the IABP group, pain severity will also be recorded immediately before IABP placement and at 12 and 24 hours post-implantation.

Laboratory Studies: The following parameters will be analyzed: hemoglobin (g/dL), hematocrit (%), platelet count, troponin (ng/mL), CK-MB (U/L), LDL (mg/dL), C-reactive protein (CRP, mg/L), glycated hemoglobin (HbA1c, %), and creatinine (mg/dL). High-sensitivity cardiac troponin I (hsCTI) levels will be measured, with the reference range of 0–0.04 ng/mL for both genders, as per our hospital's laboratory standards. hsCTI levels will be checked at admission and subsequently every 24 hours for both groups until the patient undergoes surgery.

Echocardiography (ECHO): On the first day, ECHO will be performed to assess ventricular function, ejection fraction (EF%), valve pathologies, and any ventricular abnormalities such as aneurysm or ventricular septal rupture. Follow-up ECHO will be conducted during the early postoperative period and at the first-month follow-up after discharge to reassess EF% and identify any pericardial effusion.

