Patients who demonstrate a decline in hsCTI levels or experience recurrent chest pain attacks will undergo coronary artery bypass grafting (CABG). All surgical procedures will be performed by the same surgical team using a standardized approach. Surgical Approach: The surgeries will be conducted via a median sternotomy under cardiopulmonary bypass (CPB). Complete revascularization will be achieved with the application of an aortic cross-clamp (ACC), guided by the vascular anatomy identified during angiography. Assessment of Graft

Flow: Following the removal of the ACC and the termination of CPB, transit-time flow measurement (TTFM) will be employed to evaluate the graft flow rates, ensuring optimal surgical outcomes.

In the postoperative period, the following parameters will be recorded: Mechanical Ventilation Duration (MV): Measured in hours from the patient's admission to the intensive care unit (ICU) until the cessation of mechanical ventilation. Bleeding Volume: The total amount of bleeding in milliliters during the first 24 hours postoperatively. Length of Stay in the Intensive Care Unit (ICU): The duration (in days) from the postoperative phase until the patient is transferred to the general ward. Total Length of Hospital Stay (HS): The number of days from hospital admission to discharge. Low Cardiac Output Syndrome (LCOS): LCOS will be defined as the presence of the following criteria: Requirement for high-dose positive inotropic agents (e.g., adrenaline, dobutamine, or noradrenaline) administered via continuous infusion, lactic acidosis (lactate levels >4 mmol/L), persistent hypotension and decreased or absent urine output. In-Hospital Mortality: Any death occurring within 30 days postoperatively will be classified as in-hospital mortality.

Exclusion criteria

To ensure a homogeneous distribution of risk factors between the groups and to accurately evaluate the effect of IABP on troponin levels, the following patients will be excluded from the study:

• Patients requiring emergency surgery due to iatrogenic cardiac or coronary injuries caused by angiography.

• Patients with mechanical complications of acute myocardial infarction, such as chordae rupture or ventricular septal rupture.

• Patients undergoing surgery using the off-pump or pumped beating heart method.

- Patients with peripheral arterial disease.
- Patients with renal failure.
- Patients with a history of cerebrovascular accidents.

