- · Patients presenting with acute cardiogenic shock or cardiac arrest

Preoperative IABP Application and Indications:

The primary indications for intra-aortic balloon pump (IABP) application in patients include elevated troponin levels and recurrent or persistent chest pain at rest.

Other common indications are:

- Hemodynamic instability.
- Multivessel coronary artery disease.
- Left main coronary artery disease.
- Narrow and/or tortuous coronary artery anatomy where percutaneous coronary intervention (PCI) has failed or is not feasible.

Procedure:

The IABP catheter is typically inserted into the femoral artery by cardiovascular surgeons under local anesthesia. The placement of the catheter is confirmed either in a hybrid operating room or using a portable imaging scope.

Statistical Analysis

The research will be conducted utilizing IBM SPSS 24 (IBM, Armonk, NY, USA) software and R-project version 4.2.3 for statistical analysis. The statistics will be provided in terms of mean, standard deviation, median, minimum, maximum, percentage, and count. After testing for normality, baseline characteristics of the two groups will be compared using Student's t-test or the Mann–Whitney U-test for continuous variables and chi-square or Fisher's exact tests for categorical variables. Differences between the IABP group and the control group regarding repeatedly measured outcomes will be analyzed using mixed ANOVA. The prognostic value of risk factors for in-hospital mortality will be evaluated by multivariate logistic regression analysis. The propensity score will be computed using a logistic regression model, incorporating the following covariates: age, gender, creatinine, CK-MB, hs-CTI levels, preoperative LVEF, and EuroScore II. The statistical significance level will be set at p<0.05.

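### The EF comparison has no rule for deaths or missed one-month ECHOs, and a three-visit mixed ANOVA as normally run drops those patients' earlier EFs too, with bias possible in either direction

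*Combined protocol and SAP*

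**What the plan says.** The Echocardiography (ECHO) item sets three EF readings for both groups. The baseline: "On the first day, ECHO will be performed to assess ventricular function, ejection fraction (EF". The second is taken early after surgery, and the third "at the first-month follow-up after discharge to reassess EF".

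The Statistical Analysis section states that group differences "regarding repeatedly measured outcomes will be analyzed using mixed ANOVA". It names no outcome in that sentence, but EF qualifies because it is measured at three visits in both groups. The software is given as "IBM SPSS 24 (IBM, Armonk, NY, USA) software and R-project version 4.2.3", without saying which will run this analysis.

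Mortality is a separate outcome: "Any death occurring within 30 days postoperatively will be classified as in-hospital mortality". Allocation is not random: "Based on their clinical conditions, the patients will be categorized into two groups".

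No part of the document says what happens to the EF analysis when a patient dies or misses an ECHO. A propensity score is to be computed from baseline covariates, but its use is not described.

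**The concern.** The third EF requires discharge alive, about another month of survival, and attendance. Because that visit is timed from discharge, which follows surgery, patients counted as 30-day deaths will in practice have no third EF. A classical mixed ANOVA with three visits uses only patients with all three readings, so it also discards the first-day and early postoperative EFs of those who died or did not return.

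The EF result then describes survivors who came back, although nothing in the plan labels it so. The indications listed for the balloon pump include hemodynamic instability and left main disease, so unequal mortality between the groups is a realistic prospect. If patients who die differ in EF course from those who live, unequal deletion can create or hide a group difference in recovery.

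There is also a gap between the two clocks. Mortality is counted from surgery and the ECHO from discharge. A patient who dies after day 30 but before the ECHO loses the third EF and is not counted in the defined mortality outcome.

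**Working it through.** The document gives no sample size, expected mortality, EF SD or EF effect, so there is no stated figure to reproduce. All rates and EF values below are assumptions.

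**Step 1: level versus change.** Let p be the share who die and g the gap in mean EF, survivors minus those who die. Removing the deaths raises a visit's mean by p × g. With gaps of 10 to 15 points:

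- 10% mortality: 0.10 × 10 to 0.10 × 15 = 1.0 to 1.5 points
- 4% mortality: 0.04 × 10 to 0.04 × 15 = 0.4 to 0.6 points
- difference between groups: 0.6 to 0.9 points

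This is a shift in EF level. Complete-case deletion moves the first-day mean as well, so the bias in change to one month is p × (g at one month − g on the first day). For patients who die, the one-month EF is a would-be value. With similar gaps in both groups, the between-group bias is:

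(0.10 − 0.04) × (g at one month − g on the first day)

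- same gap at both visits: 0.06 × 0 = 0
- gap 5 points larger at one month: 0.06 × 5 = +0.3
- gap 5 points smaller at one month: 0.06 × (−5) = −0.3
- gap 9 points larger at one month: 0.06 × 9 = +0.54

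**Step 2: simulation at 4% versus 10%.** Assumptions: EF SD 10; visit means 40, 42 and 45 in both groups (true difference in recovery 0); between-visit correlation 0.5 to 0.85; log-odds of death rising by 1 per SD of a worse driver; only patients with all three EFs kept. Bias is the higher-mortality group minus the lower, in EF points, for first day to one month:

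| Death driven by | Bias |
|---|---|
| Low first-day EF | −0.3 to −0.1 |
| Low early postoperative EF | about 0 |
| EF low at all visits | about 0 |
| Low would-be one-month EF | +0.1 to +0.3 |
| Poor change to one month | +0.3 to +0.5 |

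**Step 3: wider mortality gaps.** At 5% versus 15% and 10% versus 25%, under the same model, the extremes were −0.60 (low first-day EF) and +1.23 (poor change).

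**Step 4: data discarded.** Assume 100 per group, 10 and 25 deaths, all after the early postoperative ECHO. Recorded EFs are 3 × 165 + 2 × 35 = 565. Mixed ANOVA drops 2 × 35 = 70 of them (12%). With 4 and 10 deaths it drops 2 × 14 = 28 of 3 × 186 + 28 = 586 (5%).

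**Step 5: all-available-data model.** In the Step 2 scenarios a likelihood-based mixed model on every recorded EF removed the bias in the early postoperative contrast throughout. It removed the one-month bias when death depended on recorded EFs (first-day or early postoperative). It did not do so when death depended on the would-be one-month EF or on the change to it.

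**The case against.** The strongest counter-argument concerns size and direction. A reader might infer that the group with more deaths will show 0.6 to 0.9 points of false recovery. The documents do not support that. The figure is a level shift. Under the very deletion at issue it cancels from the change score when the EF deficit is the same at every visit, and the sign reverses when death tracks low first-day EF. In the scenario with the largest positive bias, patients who die start with a higher first-day EF than survivors, which sits badly with the idea that deaths simply occur in those with the lowest EF. This objection stands.

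Some premises are inferred. The mixed ANOVA sentence does not name EF, and serial troponin also fits it. Complete-case deletion is the usual behaviour of the method, not something the plan states. This stands too, but if a likelihood-based model is intended, the plan has to say so.

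EF is not designated primary and mortality is reported separately, so deaths are not concealed, and non-random group formation is the larger threat to the study. That limits the weight of this point. It does not supply the missing rule.

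On remedies, an unadjusted comparison ranking death worst would let excess deaths among sicker patients appear as an effect on EF. That is fair and confines it to a sensitivity analysis.

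**Conclusion.** The concern holds as a bias of uncertain sign and modest size, combined with an avoidable loss of recorded data. Under the assumed 4% versus 10% mortality and EF SD 10, it is about −0.3 to +0.5 EF points for change to one month. It grows with the mortality gap and with how far the EF deficit of patients who die changes between visits. It favours the group with more deaths only when death tracks poor recovery or low later EF.

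What rests on the documents is the visit schedule, the choice of mixed ANOVA, the non-random groups, and the absence of any rule for deaths or missed ECHOs. The mortality rates, SD, correlations and death mechanisms are assumptions. The change is worth making before analysis, but it does not outrank the handling of confounding.

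**What to change.** Amend the Statistical Analysis section for EF as follows:

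- Replace mixed ANOVA with a likelihood-based mixed model (group, visit, group × visit; unstructured covariance) using every available reading, and state the confounding adjustment.
- Report the first-day to early postoperative EF change as a contrast in its own right, since later death does not cut it off. Patients who die before that ECHO still lack it and should be counted.
- Label one-month EF as among survivors.
- Tabulate by group the deaths up to day 30, the deaths after day 30 but before the ECHO, and the missed ECHOs in living patients.
- As a sensitivity analysis only, with the same confounding adjustment as the main analysis, compare one-month EF by ranks with death before the ECHO ranked worst.

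The cost is SAP wording, one extra analysis and one table, with no added measurement. Two drawbacks should be stated in the plan. At one month the mixed model still extrapolates EF beyond death, so it does not settle that contrast. The rank result is not in EF points and mixes mortality with EF.

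### Troponin sampling ends at surgery and a troponin decline can trigger surgery, so a complete-case mixed ANOVA on readings past 24 h can misstate the IABP effect in either direction

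*Combined protocol and SAP*

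**What the plan says.** Laboratory Studies sets the sampling: "hsCTI levels will be checked at admission and subsequently every 24 hours for both groups until the patient undergoes surgery". The paragraph that opens the surgical description sets the trigger: "Patients who demonstrate a decline in hsCTI levels or experience recurrent chest pain attacks will undergo coronary artery bypass grafting (CABG". Statistical Analysis gives the method: "Differences between the IABP group and the control group regarding repeatedly measured outcomes will be analyzed using mixed ANOVA". It does not say which outcomes or time points are meant, or what happens to shorter series. Ejection fraction is also measured repeatedly (Echocardiography section), so hsCTI is not the only candidate.

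No primary endpoint is named, but Exclusion criteria gives as one purpose of the exclusions to "accurately evaluate the effect of IABP on troponin levels".

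All patients have a pain score on the first day. Beyond that, scores are scheduled for one group only: "For patients in the IABP group, pain severity will also be recorded immediately before IABP placement and at 12 and 24 hours post-implantation".

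**The concern.** The length of each patient's hsCTI series depends on the hsCTI values in it. A decline needs two readings, so it can first appear at 24 h. A patient who declines then and is operated on before the next sample has no 48 h value. Classical mixed ANOVA needs every reading from every patient, so adding the 48 h point removes that patient altogether. The patients left are selected on the outcome.

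If IABP lowers troponin, its responders are removed preferentially. If the groups wait different times for surgery, the selection differs by group and can create a difference where none exists. Unequal waiting is plausible: groups are formed by clinical condition, and the main IABP indications (elevated troponin, recurrent or persistent rest pain) overlap the surgical trigger. Pain-triggered surgery adds a second route out of the series, and an attack in a Group B patient has no scheduled pain score.

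**Working it through.** The plan has no sample size, SD, effect size, pain rate or interval to surgery, so there is no figure to reproduce. The sizes below are illustrative.

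**Assumed inputs.** Log hsCTI; daily changes d1 (0-24 h) and d2 (24-48 h) bivariate normal with SD s = 0.5 and correlation r from 0 to 0.8. Mean daily change m is 0 in controls (B) and -0.2 or -0.4 in the IABP group (A), giving true 0-48 h differences of -0.40 or -0.80. Any fall (d1 < 0) counts as a decline. A share q of decliners is operated on before the 48 h reading. Pain surgery removes 10% per 24 h interval, unrelated to hsCTI.

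**Formula for complete cases.**
- E1 = [E(d1; d1≥0) + (1-q)·E(d1; d1<0)] / [P(d1≥0) + (1-q)·P(d1<0)]
- Mean 0-48 h change = E1 + m + r(E1 - m)

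**Worked case: q = 0.9 in both groups, true -0.40.**
- A: E1 = (0.1152 - 0.1×0.3152)/(0.3446 + 0.1×0.6554) = 0.0837/0.4101 = 0.2041.
- B: E1 = (0.1995 - 0.1×0.1995)/(0.5 + 0.1×0.5) = 0.1795/0.55 = 0.3264.
- r = 0: (0.2041 - 0.2) - 0.3264 = -0.322.
- r = 0.8: (0.0041 + 0.8×0.4041) - 1.8×0.3264 = 0.327 - 0.588 = -0.260.
- Kept: 0.9²×0.4101 = 33% of A and 0.9²×0.55 = 45% of B.

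**Equal shares, complete-case reading at r = 0 / r = 0.8.**

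| q in both groups | True -0.40 | True -0.80 |
|---|---|---|
| 100% (extreme) | -0.265 / -0.156 | -0.515 / -0.287 |
| 90% | -0.322 / -0.260 | -0.678 / -0.580 |
| 75% | -0.368 / -0.342 | -0.774 / -0.753 |
| 50% | -0.396 / -0.393 | -0.813 / -0.824 |

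**Varying SD (0.3 to 0.8) and control drift (-0.2 to +0.2 per day).** The error goes both ways. At q = 90%, -0.40 reads -0.44 to -0.24 and -0.80 reads -1.06 to -0.50. At 75%, the ranges are -0.49 to -0.30 and -1.01 to -0.64.

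**Unequal shares, base assumptions.**
- No effect, 90% in A and 50% in B: B has E1 = (0.1995 - 0.5×0.1995)/0.75 = 0.133. The reading is 0.3264 - 0.133 = +0.193 at r = 0 and 1.8×0.1934 = +0.348 at r = 0.8. Swapping the shares flips the sign.
- No effect, 75% against 50%: +0.11 to +0.19.
- True -0.40, 90% against 50%: -0.13 to +0.09.

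**Second illustration, different assumptions** (patient-specific slopes with SD 0.4, error SD 0.2, drift -0.1 per day, 20% pain surgery). A true -0.60 reads -0.27 if all decliners are operated on in both groups, and -0.97 if the shares are 60% in A and 95% in B. With no effect, 60% against 95% reads -0.34; at 60 per group, a t-test on the complete-case 0-48 h change rejects about 34% of the time at the 0.05 level. With no effect and identical rules in both groups the reading is 0.00 and rejection about 4.5%.

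**Alternative model, by simulation under the base assumptions.** A likelihood model with unstructured covariance returns the true value within 0.01 in every equal-share case and in the 90%/50% cases. A random intercept alone does not: at 90% it gives -0.36 to -0.29 for -0.40 and -0.74 to -0.62 for -0.80, and +0.10 to +0.27 with no effect at 90% against 50%.

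**Limit of that model.** Suppose pain surgery depends on unseen hsCTI (log-odds +1 to +2 per log unit, r = 0.5). The unstructured model then gives -0.39 to -0.36 and -0.78 to -0.74. With no effect and base pain rates of 5% in A and 30% in B, it gives +0.13 to +0.24 at 48 h and +0.06 to +0.11 for 0-24 h.

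**The case against.** The point depends on choices the plan has not made: that hsCTI is an outcome for the mixed ANOVA, that readings past 24 h enter, and that the classical complete-case form is meant. If only admission and 24 h are analysed, decline-triggered surgery removes nobody. That is right, and the concern is conditional for that reason. But daily sampling runs until surgery and nothing restricts the analysis to 24 h.

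The sizes are assumed. With equal shares under the base assumptions, the error is small at 75% and negligible at 50% for a true -0.40. The plan says such patients will be operated on but not how soon, and it does not define a decline. Counting any fall is influential and was not varied. This stands: the mechanism and both directions are established, the size is not.

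The proposed model succeeds partly by construction, because in most scenarios stopping depends only on recorded hsCTI or on chance. This also stands. When pain surgery tracks unseen hsCTI and is far commoner in one group (5% against 30%, 90% share, no effect), complete cases read +0.135 and +0.251 and the likelihood model +0.134 and +0.233, almost no gain. That is why the fix includes a sensitivity analysis.

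Finally, unstructured covariance over many daily readings may be unstable: seven readings need 7×8/2 = 28 covariance parameters. Limiting the model to time points named in advance answers much of this.

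**Conclusion.** The concern holds as stated. Sampling that stops at surgery, surgery triggered by the sampled marker, and an analysis that in its classical form requires complete series together select patients on the outcome once readings past 24 h are used. The documents do not fix the direction or size of the error. In the illustration it runs from negligible (both groups at 50%) to the loss of about 20% to 35% of a true -0.40 (both at 90%: 0.078/0.40 to 0.140/0.40), and to a spurious difference of 0.19 to 0.35 log units when the shares are 90% and 50%. Decline-triggered truncation causes no bias if only admission and 24 h are analysed, or if there is no effect, the groups are comparable and both wait equally long. This should be settled before analysis; it is separate from confounding by indication, which remains under any of these models.

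**What to change.** In Statistical Analysis, for hsCTI:

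- Replace mixed ANOVA with a likelihood-based linear mixed model on log hsCTI, with group, categorical time and group-by-time as fixed effects and unstructured covariance, not a random intercept alone. Keep every patient, including those with short series.
- Name the time points in advance, and report the admission-to-24 h contrast alongside as the one least affected by truncation.
- Record the reason for surgery (decline or pain), and report the number sampled at each reading by group and reason.
- Add a sensitivity analysis that shifts the unseen readings of patients operated on for pain, separately by group. The range is an assumption to state, for example 0 to +0.5 log units.
- State that the model is valid only if stopping depends on recorded data, and that it addresses truncation, not confounding by indication.
- Separately, if the balloon is placed after the admission reading, use the placement time to code earlier readings as unexposed.

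The surgical trigger is left as it is. The cost is SAP wording, one recorded item and one sensitivity analysis. No blood samples are added, placement time is already needed for the 12 h and 24 h pain scores, and the named software can fit the model. The drawback is possible non-convergence if late readings are sparse. Precision does not suffer materially in the illustration: with an assumed 50 per group, a 90% share, correlation 0.5 and a true -0.40, the SD of the 48 h estimate is 0.22, against 0.24 for complete cases.

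### No IABP-specific complication and no new stroke is recorded, and bleeding and death are counted only after surgery, so harm attributable to the preoperative device cannot be quantified

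*Combined protocol and SAP*

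**What the plan says.** The combined protocol and SAP describes the device under the Procedure heading: "The IABP catheter is typically inserted into the femoral artery by cardiovascular surgeons under local anesthesia". Support starts before surgery, and that preoperative support is the exposure under study.

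The outcomes stand in the unnumbered paragraph just before the exclusion criteria, which opens: "In the postoperative period, the following parameters will be recorded". Six items follow: duration of mechanical ventilation, bleeding volume, ICU stay, hospital stay, low cardiac output syndrome (LCOS) and mortality. Two of the definitions fix a time window that begins at surgery:

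- "Bleeding Volume: The total amount of bleeding in milliliters during the first 24 hours postoperatively"
- "In-Hospital Mortality: Any death occurring within 30 days postoperatively will be classified as in-hospital mortality"

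Hospital stay has a wider window: "Total Length of Hospital Stay (HS): The number of days from hospital admission to discharge".

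Elsewhere the document records pain scores, laboratory values, echocardiography and graft flow. It has no adverse-event section. Limb ischaemia, vascular injury, access-site bleeding, device infection, device malfunction and new stroke are not named as outcomes anywhere.

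**The concern.** An invasive device can help and can also injure. A study whose full title speaks of advantages needs both sides of that balance. Here the period in which the device is in place and surgery has not yet happened has no harm outcome at all. A groin haemorrhage, an ischaemic leg or a stroke between insertion and surgery would have no field to go into. A patient who died before reaching surgery would fall outside the mortality definition as worded.

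At stake is what the study can conclude. If Group A does better on the listed outcomes, nothing can be said about the price in device complications. If Group A does worse, nothing in the data would help to tell a device effect from sicker patients.

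**Working it through.** The plan states no figure on this point, so there is none to reproduce. The check is a reading of every recorded item against two questions: is it specific to the device, and could it come out worse with the device?

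**Postoperative list**

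| Item | Device-specific? | Could be worse with IABP? | Window |
|---|---|---|---|
| Ventilation time | No | Yes | From ICU admission |
| Bleeding volume | No | Yes | First 24 h after surgery |
| ICU stay | No | Yes | After surgery |
| Hospital stay | No | Yes | From admission |
| LCOS | No | Yes | After surgery |
| Death | No | Yes | 30 days after surgery |

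The count is 0 of 6 device-specific and 6 of 6 able to show a worse result. Only hospital stay reaches back before surgery, and it is a duration, not an event.

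**Between insertion and surgery.** The measurements with stated times while the device is in place are pain (just before placement, then at 12 and 24 hours) and high-sensitivity troponin every 24 hours until surgery. Both address the intended effect. Neither would register a limb, access-site or neurological event.

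**Laboratory values.** The list includes "hemoglobin (g/dL), hematocrit (%), platelet count, troponin (ng/mL), CK-MB (U/L), LDL (mg/dL), C-reactive protein (CRP, mg/L" and creatinine. A fall in haemoglobin or platelets might hint at a complication, but serial timing is given only for troponin, and no complication is defined from any of these values.

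**Attribution.** The introduction assigns patients to Group A or B by clinical condition. The section on preoperative IABP application lists indications such as raised troponin, persistent chest pain at rest and haemodynamic instability. A worse general outcome in Group A could therefore reflect the indication. A complication at the device's own access site is much easier to attribute.

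**What recording would buy.** The documents give neither a sample size nor a complication rate, so the group sizes below are assumptions. With 0 events in n patients, the exact two-sided 95% upper limit is 1 − 0.025^(1/n):

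- n = 100: 1 − 0.025^(1/100) = 0.036, about 3.6%.
- n = 50: 1 − 0.025^(1/50) = 0.071, about 7.1%.

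Even a count of zero would therefore be informative. Without the field there is neither a count nor a limit.

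**The case against.** The strongest reply is that harm does have routes into the data. All six postoperative outcomes can be worse with the device. Bleeding is a total that is not restricted by site ("The total amount of bleeding in milliliters during the first 24 hours postoperatively"), so femoral bleeding after surgery is not clearly left out. Hospital stay runs from admission, so a preoperative complication that delays discharge could lengthen it. Physical examination findings and blood counts are recorded too. All of this stands. It shows that net harm could appear. It does not show that harm due to the device could be recognised or counted.

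Three stronger readings are tempting, and the documents do not support them:

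- A reader might infer that the study can show only benefit or no difference. It cannot be said to: every listed outcome can go either way, the Statistical Analysis section sets p<0.05 without a one-sided test, and mixed ANOVA is not directional. The full title presupposes advantages, but the brief title is neutral, and no directional hypothesis or decision rule is stated.
- A reader might infer that the exclusions of peripheral arterial disease and prior cerebrovascular accident were a way of hiding harm. They apply to both groups, and the stated purpose is balanced risk factors and a clean evaluation of troponin. They limit to whom a complication rate would apply; they are not a fault in outcome recording.
- A reader might infer that access-site complications are the principal way the device could be worse. The documents do not rank harms, so the point cannot rest on that.

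**Conclusion.** The gap is real but narrower than a claim of a one-directional study. No device or access-site complication and no new stroke is among the recorded outcomes, and the recorded bleeding and death outcomes start at surgery. Harm attributable to the preoperative device therefore cannot be identified or quantified. Only non-specific outcomes could reveal net harm, and in groups formed by clinical condition these are hard to assign to the device. A conclusion of advantages would rest on an incomplete benefit-risk picture.

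The number of events that would go unrecorded cannot be stated from the documents. The limits of 3.6% and 7.1% only illustrate precision under assumed Group A sizes of 100 and 50, and the finding does not depend on them. It should be corrected because the remedy is cheap and changes what the study can conclude.

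**What to change.** Add two blocks to the postoperative outcome paragraph, with a definition for each event.

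1. **Both groups, from hospital admission to 30 days after surgery:** limb ischaemia; vascular injury or bleeding away from the surgical site that needs treatment; new stroke; and death before surgery. Report by group as counts with exact two-sided 95% confidence intervals. Admission is the common origin; starting at insertion in one group and admission in the other would give unequal windows. Record event dates so that Group A events before insertion can be told apart.
2. **Group A only, from insertion to 30 days after surgery:** IABP access-site bleeding or vascular injury, device-site infection and device malfunction. Report as counts with exact two-sided 95% confidence intervals. Group B has no device, so these events have no comparator there.

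This changes what is written down, not how patients are managed. The cost is a few extra data fields. Group A is already assessed at 12 and 24 hours after implantation, and a first-month visit after discharge is already planned, so contact points exist. That the rest can be taken from existing charts is an assumption, since the documents do not describe data sources. The other downside is that the published result may look less favourable.
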